6.7 BASELINE, TIME WINDOWS AND CALCULATED VISITS

Study days and visits will be labelled according to the flow chart of the CTP.

Unless otherwise specified, baseline is defined as the time-point closest to but prior to first administration of trial medication in the first treatment phase, where the first administration

of trial medication is defined in [Section 6.3](#) above. If this criterion is not fulfilled, then no baseline will be derived.

For laboratories where not only the examination date but also time is recorded, examination time has to be taken into account when defining baseline. That is, a laboratory value on the same date as the first study drug administration is considered as baseline value if and only if the time of laboratory value is before or the same as the date and time of the start of first study drug administration.

If any of these times are missing (either no time of start of first study drug administration or no lab sample stating that it was taken prior to start of first study drug administration) and so it cannot be concluded whether the blood sampling was done before or at the same time of the start of first study drug administration, the last available laboratory assessment before first study drug administration will be taken (Screening laboratory) .

For graphical presentations of laboratory data, baseline will be coded as Day = 1.

The definition of relative baseline for the investigation of laboratory signs of cell destruction is given in [Section 5.4.5.2](#).

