## FLOWCHARTS

### Flowchart for Course 1

Trial Periods	Screen	Treatment and observation/rest										EOT	FU
Course *		1											
Week		1		2		3		4		5		6	7
Visit **	Screen	1	2	3	8	9	10	15	17	22	29	36	43
Days	-14 to -1	1	2	3	8	9	10	15	17	22	29	36	43
Informed consent	x												
Demographics	x												
Medical history	x												
Review of in-/exclusion criteria	x	x 1											
Eligibility for trial	x												
12-lead ECG	x												
Height	x												
Weight	x	x	x	x	x	x	x	x	x	x	x	x	
Physical examination, incl. tumour size (lymph nodes, spleen, liver),	x	x								x			x
Vital signs 	x	x	x	x	x	x	x	x	x	x	x	x	x
Dose assignment	x 												
Concomitant therapy	x	x	x	x	x	x	x	x	x	x	x	x	x
General safety laboratory parameters 	x	x	x	x	x	x	x	x	x	x	x	x	x
Administration of BI 836826		x		x			x		x	x			
Screening for Tumour Lysis Syndrome 		x	x		x	x							
Adverse events		x	x	x	x	x	x	x	x	x	x	x	x
Disease/response assessm. (clinical/imaging)	x	x 6							x 				x 
Serum pregnancy test 	x	x							x				
CMV monitoring 	x	x					x		x	x	x	x	x
Lymphocyte typing (B/T/NK cells)		x		x	x		x	x	x	x	x	x	x
Virology screening  (HBV, HCV, HIV, CMV)	x												
CT scan of neck, thorax, abdomen and pelvis	x 												

Proprietary confidential information.

© 2016 Boehringer Ingelheim International GmbH or one or more of its affiliated companies. All rights reserved.

This document may not - in full or in part - be passed on, reproduced, published or otherwise used without prior written permission.

EOT: End of treatment visit, to be performed at withdrawal from further treatment (<12 administrations) or at the latest 8 weeks after the last administration of BI 836826 (12 administrations)

FU: Follow-up visits (starts after EOT) at least every 6 weeks until 6 months after EOT visit, details see [section 6.2.3.2](#)

CMV: Cytomegalovirus

HBV: Hepatitis B virus

HCV: Hepatitis C virus

HIV: Human immunodeficiency virus

\* the planned duration of course 1 is 7 weeks (49 days)

\*\* the visit number follows the course number, i.e. visit 2 course 1 will read C1\_V2 and visit 2 course 2 will read C2\_V2 ...

- 1 Review of eligibility
- 2 For details during and after infusion of BI 836826, refer to [section 5.2.5.1](#)

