#### 4.1.4.4 Continuation of Treatment during a Course, or beginning a new course

Adverse events and laboratory values will be evaluated continuously by the sponsor. Prior to each administration of BI 836826, adverse events and safety laboratory will be assessed. To

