## **5.2.3 Assessment of safety laboratory parameters**

### **5.2.3.1 General safety laboratory parameters**

Blood samples and urine have to be collected at the time points specified in the [flowchart](#). Safety laboratory examinations will include haematology, biochemistry, coagulation and qualitative urine analysis.

Haematology	Haemoglobin, red blood cell count (RBC), white blood cell count (WBC) with differential, platelets (PLT)
	Reticulocytes have to be measured only at visit of the first and last administration of each treatment course, at the EOT visit and during follow-up.
Biochemistry	Glucose, sodium, potassium, calcium, inorganic phosphate, creatinine, aspartate amino transferase (AST), alanine amino transferase (ALT), alkaline phosphatase (AP), lactate dehydrogenase (LDH), total bilirubin (if elevated provide direct bilirubin), urea, total protein, albumin, uric acid
	Serum immunoglobulin levels (IgG, IgM, IgA), direct antiglobulin test have to be measured only at visit of first and last administration of each treatment course, at the EOT visit and during follow-up.
Coagulation	Activated partial thromboplastin time (aPTT), prothrombin time (PT)/international normalised ratio (INR)

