6.6 HANDLING OF MISSING DATA AND OUTLIERS

If not stated otherwise, missing data will not be imputed and remain missing. Potential outliers will be reported and analysed as observed.

Missing or incomplete AE dates are imputed according to BI standards (see [\(5\)](#)).

Missing data and outliers are handled according to 001-MCS-36-472 [\(2\)](#).

If the day of birth is missing, then the imputed days will be the 15th. If start of new NHL therapy date is incomplete (only month given), then the start date will be imputed with the 1st of month unless the first day leads to a date before the stop date of study medication, then the study medication stop date +1 will be imputed. If more than only the day is missing, dates will not be imputed.

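### The screening-laboratory fallback in SAP 6.7 leaves lymphocyte subsets, immunoglobulins, the direct antiglobulin test and reticulocytes without a baseline, because none of them has a scheduled screening sample

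*SAP*

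**What the plan says.** SAP 6.7 defines baseline as the time-point closest to, but before, the first administration. If nothing qualifies, "If this criterion is not fulfilled, then no baseline will be derived". Where laboratory times are recorded, a same-day value counts only if it is timed at or before the start of the first dose. The fallback applies when the infusion start time is missing or there is "no lab sample stating that it was taken prior to start of first study drug administration", so that the order cannot be concluded. In that case "the last available laboratory assessment before first study drug administration will be taken (Screening laboratory"). SAP 6.6 adds that, unless stated otherwise, "missing data will not be imputed and remain missing". Protocol 7.4 also replaces a missing baseline laboratory value with the screening value.

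The sampling schedule is in the protocol. In the Course 1 flowchart, and again in the split-dose flowchart of Appendix 10.7.1, the row "Lymphocyte typing (B/T/NK cells") has no mark at screening and its first mark on Day 1. The general safety laboratory row is marked at screening, but its footnote refers to section 5.2.3.1, which restricts some components. "Reticulocytes have to be measured only at visit of the first and last administration of each treatment course", at EOT and in follow-up. Immunoglobulins and the direct antiglobulin test likewise "have to be measured only at visit of first and last administration of each treatment course", at EOT and in follow-up.

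SAP 7.8.2 plans change from baseline for all laboratory parameters and CTCAE grade changes from baseline to the last and to the worst on-treatment value. SAP 5.4.5.1 lists the CD4+ T cell count among the prioritised laboratory values.

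**The concern.** A fallback is useful only if it points to a sample that exists. For these parameters Day 1 of Course 1 is the only scheduled pre-treatment sample. If it is set aside for lack of a usable time, SAP 6.7 turns to a screening value that the protocol does not schedule.

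The drug depletes B cells, and infections at 100 mg are the reason for the Korean cohorts, so readers of the trial report will look for change in CD4+ cells, B cells and immunoglobulins. A patient without a baseline cannot contribute to those summaries. The Day 1 value set aside does not disappear: it falls within the on-treatment window and is then handled as a post-baseline value, although it was probably drawn before the drug was given.

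**Working it through.** The plan gives no figure to reproduce. The check sets the baseline rule beside the sampling schedule.

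| Parameter | Scheduled at screening? | First scheduled sample | Does the fallback return a value? |
|---|---|---|---|
| Lymphocyte subsets (Course 1 flowchart, Appendix 10.7.1) | No | Day 1 | No |
| Reticulocytes (5.2.3.1) | No | First administration | No |
| IgG, IgA, IgM (5.2.3.1) | No | First administration | No |
| Direct antiglobulin test (5.2.3.1) | No | First administration | No |
| Neutrophils, WBC, total lymphocytes, platelets, LDH, uric acid | Yes, in the general safety laboratory | Screening | Yes |

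Protocol 5.2.3.4 names B, CD4+, CD8+ and NK cells. SAP 5.4.5.1 adds CD3+; I take it to come from the same typing sample.

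**Consequence, step by step.**

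1. The Day 1 sample cannot be ordered against the infusion start, so SAP 6.7 sets it aside.
2. No screening sample is scheduled, so no baseline is derived unless an unscheduled earlier value exists. SAP 6.6 leaves it missing, and Protocol 7.4 points to the same absent screening value.
3. Change from baseline cannot be calculated for that patient and parameter.
4. The two grade shifts that start from baseline are lost where a grade exists. SAP 7.8.2 uses CD4+ Grade 4, so CD4+ is affected. SAP 5.4.5.1 states that immunoglobulins and the direct antiglobulin test have no CTCAE grade, so no informative shift is lost for them.
5. SAP 7.8.2 applies the adverse-event treatment periods to laboratory data, and SAP 6.1 starts these at the treatment start date. The Day 1 value therefore counts as on-treatment. As it is not the baseline, it is post-baseline.

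**Could these Day 1 values be confused with later samples on the same day?** Protocol 5.2.3.2 schedules repeated tumour lysis sampling every 4-8 hours after infusion start. That panel holds blood counts with differential, uric acid, potassium, calcium, phosphate, LDH, creatinine and urea. None of the parameters without a screening sample is in it.

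**Size.** The share of Day 1 samples with unknown order is not stated. For one affected patient:

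- cohort of six: 1/6 = 17%
- cohort of three: 1/3 = 33%

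As an illustration, let *m* be an assumed share, with losses independent between patients. The expected loss among the planned 53 patients is 53 × *m*, and the chance that a cohort of six loses at least one baseline is 1 − (1 − *m*)^6.

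| *m* (assumed) | 53 × *m* | 1 − (1 − *m*)^6 |
|---|---|---|
| 2% | 1.1 | 11% |
| 5% | 2.7 | 27% |
| 10% | 5.3 | 47% |
| 20% | 10.6 | 74% |

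If missing times cluster by laboratory, losses are not independent and the last column does not apply.

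**The case against.** The strongest reply is that the trigger is narrow. It applies only when the order cannot be concluded, and a sample labelled pre-dose remains usable. Protocol 4.1 requires the actual infusion start time in the eCRF. No passage shows that sampling times are missing, and declining to derive a baseline of unknown timing is a defensible conservative choice. This stands as a limit on frequency. It does not make the fallback work when it is needed. The explicit instruction to record sample date and time stands in the tumour lysis section (5.2.3.2); the lymphocyte typing section (5.2.3.4) has none and refers to a laboratory manual. That manual and the sponsor's internal laboratory standards are not among the documents and could settle the point.

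Several stronger readings are tempting but not supported:

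- A reader might infer that every patient at a laboratory recording dates only loses the baseline. The fallback paragraph follows on from the case where times are recorded. SAP 6.7 does not say how a same-day sample with a date only is treated, and no document shows that such a laboratory takes part.
- A reader might infer that these parameters are never available before treatment. They are not scheduled; an unscheduled earlier value would qualify.
- A reader might infer that the analysis of infections is lost. CD4+ Grade 4 episodes with concomitant infections, the worst-to-last grade change and the time-course plots need no baseline.
- A reader might take the Day 1 typing sample to be pre-dose by design, because Protocol 4.1.4.4 says "Prior to each administration of BI 836826, adverse events and safety laboratory will be assessed". Section 5.2.3.1 defines the general safety laboratory as haematology, biochemistry, coagulation and urine, and typing has its own section and flowchart row. The sentence makes a pre-dose draw likely for typing but does not establish it.

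**Conclusion.** The concern holds in a limited form. For lymphocyte subsets, reticulocytes, IgG, IgA, IgM and the direct antiglobulin test, the SAP 6.7 fallback leads to a screening sample that the protocol does not schedule, while SAP 7.8.2 still plans change from baseline for all laboratory parameters. Protocol 7.4 has the same gap.

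The loss is confined to patients whose Day 1 sample cannot be ordered and who have no unscheduled earlier value. Among the affected parameters only CD4+ is prioritised. The per-cohort figures of 17% and 33% assume exactly one affected patient; how often that would happen is unknown, and the wider range above rests on assumed rates. All affected analyses are descriptive, and determination of the MTD and the DLT counts do not use these baselines. This is a cheap improvement to the SAP, not a threat to the trial's main conclusion.

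**What to change.** Add a rule to SAP 6.7 that applies only to parameters with no scheduled screening sample:

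- If the order of the Course 1 Visit 1 sample relative to the infusion start cannot be established, use that sample as baseline, unless there is evidence that it was drawn after infusion start.
- Flag these baselines in the listing and report their number per cohort.

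Keep the screening fallback for every parameter that has a screening value. Extending the new rule to all parameters would replace a value known to be pre-drug with an untimed one, on a day when tumour lysis samples are drawn repeatedly after infusion start. Leave unchanged the SAP 7.8.2 rule that includes the baseline value in the on-treatment period; the change affects only whether the sample is labelled baseline or post-baseline.

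The cost is a short addition to the SAP and a small programming change. The downside is that an occasional post-infusion sample may be taken as baseline and so understate the drug effect in that patient; the flag makes such cases visible.

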7. PLANNED ANALYSIS

For end-of-text (EoT) tables, the set of summary statistics is: N / Mean / standard deviation [StD] / Minimum [min] / Median / Maximum [max].

For tables that are provided for endpoints with some extreme data, median, quartiles and percentiles should be preferred to mean, StD, min and max.

For time-to-event analysis tables, the set of statistics is: number of patients [N(%)], Number of patients with event [N(%)], <Time to event> [months] followed by P25 (25th percentile), median, P75 (75th percentile), Number of patients censored [N(%)]. If not specified otherwise, the duration as well as the time to event will be displayed in days and a final decision will be made at the last BRPM.

Tabulations of frequencies for categorical data will include all possible categories and will display the number of observations in a category as well as the percentage (%) relative to the respective treatment group (unless otherwise specified, all patients in the respective patient set whether they have non-missing values or not). Percentages will be rounded to one decimal place. The category missing will be displayed only if there are actually missing values. The denominator of the main categories is defined by the number of patients in the used patient set. The main categories define the denominators of the subcategories. Subcategories should be intended and “[N(%)]” will be displayed only for the main category. If a table includes only categorical data, “[N(%)]” is to be displayed in the column header.

If applicable, conversion from days to weeks, months and years will be as follows:

- Weeks = Days/7
- Months = (Days × 12)/365.25
- Years = Days/365.25

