6.3 PATIENT SETS ANALYSED

The Screened Set (SCR) includes all patients who signed informed consent form and will be used to summarize patient disposition.

The Treated Set (TS) consists of all patients who received at least one application of the BI drug BI 836826. The TS will be used for all planned safety analyses.

Replacement of patients is defined in Section 3.3.4.1 in the CTP. The final list of replaced patients is supplied by the Trial Clinical Monitor (TCM) no later than at the last BRPM before the DBL.

No per protocol population will be used for analyses.

Study medication is defined as BI 836826.

First administration of study medication is defined as date of first administration of BI 836826.

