7.8.1.2 Adverse events

AE analysis will be performed for all treatment periods and selected analyses for the MTD evaluation period.

The analyses of AEs will be descriptive in nature and will follow the standard procedure laid down in the Data Management and Statistics Manual (DM & SM) (including all required tables and listings) (current guideline 'Handling and Summarization of AE Data for CTR and Integrated Summaries' (6)). AEs will be coded with the most recent version of Medical Dictionary for Regulatory Activities (MedDRA). The version number will be displayed as a footnote in the respective tables and listings. The SOC will be sorted alphabetically, and PTs will be sorted by descending frequency of adverse events in the "Total" BI 836826 group

Each patient can be observed during the trial under several doses. Analysing the AE of all treatment courses will be carried out under the initial treatment. No formal statistical analysis is planned for the safety comparison.

The analysis of AEs will be based on the concept of treatment emergent AEs. That means that all AEs occurring between the first administration of BI 836826 until 8 weeks after last administration of BI 836826 will be assigned to the on-treatment period. AEs will be distinguished for the treatment course in which the subjects are on-treatment as well as for screening, and post-study. The actual planned dosage of BI 836826 administered on the day each AE starts will also be derived and will be included in the listing. Listings of screening events will not be sorted by initial treatment. Post-study listings will be sorted by initial treatment.

According to the BI standards, multiple recordings of AEs will be collapsed to episodes on the lowest level term and multiple episodes will be condensed to records on the PT and SOC level. CTCAE grade will be an additional criterion for collapsing and condensing AEs. The maximum CTCAE grade will be assigned to episodes and records. CTCAE grade and DLT information will be displayed in AE listings. MedDRA levels for condensing will be SOC and PT.

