7.8.1.5 Infusion-related reactions (IRR)

Frequency of IRRs will be displayed in separate listings and tables where it will be differentiated between the reported AE term "Infusion-related reaction" and the symptoms of an IRR that are reported as AEs.

For patients at the beginning of this trial (up to the 50 mg dose cohort (enrolment before April 2013)), the symptoms of an IRR are reported as AEs but not captured explicitly as symptoms of an IRR. For these patients, potential symptoms of an IRR can be only identified by pre-defined AE preferred terms as given by the user-defined category . For patients from following dose cohorts (including some patients of the 50mg cohort), not only IRRs are reported with the AE term "Infusion-related reaction" but also its symptoms which are

additionally marked as symptoms of an IRR. IRR tables capturing IRR symptoms can be only displayed for these patients. A listing will show all patients with IRR episodes as well as reported symptoms of these IRRs. Furthermore symptoms of IRRs will also be displayed where it will be distinguished between symptoms marked as such and potential symptoms of an IRR.

The number of episodes of IRRs as well as the frequency of its symptoms and CTCAE grades will be displayed graphically for those patients where the symptoms of an IRR are reported as such.

The frequency of the AE “Infusion-related reaction” episodes based on the preferred MedDRA term will be displayed by administration visit together with its CTCAE grade for all patients.

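### The by-visit display of infusion-related reactions has no at-risk denominator, so under the SAP default any percentage at later visits is biased downward by the share of patients no longer infused

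*SAP*

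**What the plan says.** SAP 7 sets the general rule for frequency tabulations. They show a count and a percentage relative to the treatment group, taken over "unless otherwise specified, all patients in the respective patient set whether they have non-missing values or not". It adds that "The denominator of the main categories is defined by the number of patients in the used patient set", and that "The main categories define the denominators of the subcategories".

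SAP 6.3 fixes the set: "The TS will be used for all planned safety analyses". The Treated Set is everyone who received at least one application of the drug. SAP 6.1 presents results by dose cohort, with Korean and Caucasian patients separate, and in total.

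SAP 7.8.1.5 says the frequency of infusion-related reaction episodes "will be displayed by administration visit together with its CTCAE grade for all patients". It names no other denominator.

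Protocol 3.1 allows up to 12 infusions in three courses of four. Course 2 is open to patients without clinical progression who tolerate the drug. Course 3 needs response, or stable disease with clinical benefit, and again good tolerability. Protocol 4.1.4.2 says patients with a grade 4 reaction are not to be given the drug again.

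SAP 7.8.2 does use the number of infusions as a divisor, but only for episodes of low blood counts.

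**The concern.** A by-visit table of infusion reactions is read for one purpose: to see whether reactions become rarer or milder after the first infusions. Protocol 5.2.5.1 expects them mainly at the first and second administration, and this table is the display that could check that expectation.

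Under the default rule, a patient who stopped after course 1 remains in the denominator at infusions 5 to 12, where a reaction was impossible. The percentage at those visits then mixes two things: the risk among patients actually infused, and the proportion still infused. The second shrinks by design. The distortion also runs towards the expected answer, so a reader who sees a decline could take it as confirmation when part or all of it is patients stopping.

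**Working it through.** **The plan's own figure.** The documents give no reaction frequency and no number infused per visit. The one related figure is the expected total in Protocol 7.6: 41 enrolled + up to 12 more = 53, which reproduces. It is an upper bound for the denominator in the total column.

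**Formula.** Let N be the patients treated, n the patients infused at a visit, and p the risk of a reaction among those infused.

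- Percentage under the SAP default = p × n / N.
- Percentage among those at risk = p × n / n = p.
- Factor of understatement = N / n, the inverse of the share still infused.

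N enters only through the share n / N, so the percentages below are the same for 41 or 53 treated.

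**Assumed inputs (not in the documents).** Share still infused at the start of course 2: 80% to 50%. Share at the start of course 3: 50% to 15%. Risk per infusion visit: 20% or 50%, held constant to isolate the effect of the denominator.

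| Visit | Share infused | Shown if risk is 20% | Shown if risk is 50% | Understated by |
|---|---|---|---|---|
| First infusion, course 1 | 100% | 20.0% | 50.0% | 1.00 |
| First infusion, course 2 | 80% to 50% | 16.0% to 10.0% | 40.0% to 25.0% | 1.25 to 2.00 |
| First infusion, course 3 | 50% to 15% | 10.0% to 3.0% | 25.0% to 7.5% | 2.00 to 6.67 |

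Example for one cell: 0.20 × 0.15 = 3.0%, and 1 / 0.15 = 6.67. With the number infused as denominator, every cell in a column would read 20% or 50%.

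**Within one dose cohort.** Take 6 treated patients and 2 reactions at the first infusion: 2/6 = 33.3%. At a later visit 3 are infused and 1 reacts. The default shows 1/6 = 16.7%; the at-risk figure is 1/3 = 33.3%, unchanged.

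**Direction.** The bias is downward, but the displayed series need not fall. If the risk rose from 20% to 50% while half were still infused, the display would go from 20% to 0.50 × 0.50 = 25%. The rise would be understated, not reversed.

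**The case against.** The best case for leaving the text alone has five parts.

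- SAP 7.8.1.5 speaks of episodes, while the SAP 7 rule is written in patients. The display may turn out to be counts, and a fall in counts is not caused by the percentage rule. This stands as a limit: the bias applies to any percentage shown. But SAP 7 asks for percentages beside counts in frequency tabulations, and counts without the number infused cannot show waning either.
- The default yields to other specification, and a row for patients infused at the visit, used as a main category, would give the at-risk percentage under the existing rule. True, but SAP 7.8.1.5 does neither. Table shells and the sponsor's internal guideline are not public and might settle it.
- The number infused can be rebuilt from planned listings of doses and administrations (SAP 7.3 and 7.7). That allows a check but does not correct the table.
- The trial is descriptive, and infusion reactions are excluded from the DLT definition in Protocol 5.2.1.1. No dose decision is shown to depend on this table. This stands and limits the weight of the point.
- Patients still infused are selected, so the at-risk percentage is not the risk for all treated patients. This also stands, and the fix should say so.

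A reader might extend the point to adverse events by treatment course, because SAP 7.8.1.2 says "AEs will be distinguished for the treatment course in which the subjects are on-treatment as well as for screening, and post-study". The documents do not support that. The same section says "Analysing the AE of all treatment courses will be carried out under the initial treatment", and its list of frequency tables runs by treatment, grade, system organ class and preferred term, not by course. An argument from unequal course lengths (49, 49 and 84 planned days) fails with it. The on-treatment window closes 8 weeks after the last dose, so a third course given on schedule ends at about day 22 + 56 = 78, the same day as for a patient who stops after the four infusions of course 1. The SAP also does not say to which course that 8-week tail belongs.

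**Conclusion.** The point holds for the by-visit display of infusion-related reactions. Followed as written, the plan gives percentages at later visits that are diluted by the share of patients no longer infused, and real waning cannot be separated from stopping.

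The mechanism follows from the text; its size does not. At the assumed shares the understatement is 1.25 to 2.0 times at the start of course 2 and 2.0 to 6.67 times at the start of course 3. These figures rest on assumed attrition and a constant risk, and the protocol itself expects risk to be highest early, so a true decline may be present as well. A reader might infer that the displayed frequency must fall with time on drug; the documents support only a downward bias. No primary conclusion is affected.

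**What to change.** In SAP 7.8.1.5, override the default: at each administration visit the denominator is the number of patients who received that infusion, by dose cohort and in total, with that n printed in the table. If the display is kept as counts of episodes, print the same n beside them. Add a footnote that patients still infused at later visits are selected for tolerability and lack of progression, so later percentages describe those patients and not everyone treated.

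This changes SAP wording and one table shell. Protocol 4.1 already requires start and end times of each infusion in the eCRF, so no new data are needed. The downside is that late-visit percentages will rest on very few patients, especially within cohorts, and should be read with their n.
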